12.1 Definition of an Adverse Event

An AE is any untoward medical occurrence in a subject or clinical investigation subject administered a pharmaceutical product that does not necessarily have a causal relationship with this treatment. An AE can therefore be any unfavorable and unintended sign, symptom, or disease temporally associated with the use of study drugs, whether or not considered related to the study drugs

12.2 Definition of a Serious Adverse Event

A SAE is defined as any untoward medical occurrence that at any dose:

- Results in death.
- Is life-threatening.
- Requires hospitalization or prolongation of existing hospitalization.
- Results in persistent or significant disability or incapacity.
- Is a congenital anomaly or birth defect.
- Is an important medical event.

Medical and scientific judgment should be exercised in deciding whether an AE is serious and whether expedited reporting is appropriate in other situations, such as important medical events that may not be immediately life threatening or result in death or hospitalization but may jeopardize the subject or may require medical or surgical intervention to prevent one of the other outcomes listed in the above definition. These should also be considered serious. Examples of such events are invasive or malignant cancers, intensive treatment in an emergency room or at home for allergic bronchospasm, blood dyscrasias or convulsions that do not result in hospitalization, or development of medication dependency or medication abuse. These should also usually be considered serious.

The term 'life threatening' refers to an event/reaction in which the subject was at risk of death at the time of the event/reaction; it does not refer to an event/reaction which hypothetically might have caused death if it were more severe.

Admission to a hospital as a new subject is deemed as meeting this criterion, even when the length of hospital stay was less than 24 hours. Transfer to other departments of the same hospital due to a newly emerged event during the hospitalization (e.g., transfer from the psychiatry ward to the internal medicine ward, from the internal medicine ward to the coronary intensive care unit, or from the neurology ward to the tuberculosis ward) is also counted as hospitalization.

SAEs will be recorded and reported as described in Section 12.8.

12.3 Adverse Events of Special Interest

One AESI that will be considered during this study includes hepatic AESIs, defined as

- Develop liver dysfunction defined as any one of the following:
 - ALT or AST $>8 \times$ ULN.
 - ALT or AST $>5 \times$ ULN for more than 2 weeks.
 - Elevated total bilirubin $>2 \times$ ULN and ALT or AST $>3 \times$ ULN or
 - Symptoms consistent with liver dysfunction (e.g., fatigue, nausea, vomiting, abdominal pain or tenderness, fever, rash, eosinophilia $>5\%$) with concomitant ALT or AST values $>3 \times$ ULN.
- Hepatic AEs or hepatic laboratory abnormalities that lead to study medication interruption or discontinuation (see Section 8.5).
- Any other laboratory or clinical abnormality that Sponsor Medical Monitor and/or Investigator considered as significant.

12.3.1 Management and Evaluation of Hepatic Adverse Events of Special Interest

Hepatic AESIs should be treated per the Investigator's approved standard of care and assessed for possible alternative etiology(ies). Hepatic AESIs will be followed clinically until resolution.

Subjects meeting the laboratory criteria of ALT/AST and total bilirubin defined in Section 12.3 (with or without alternative etiology), regardless of whether clinically significant or not, should be reported as a hepatic AE of special interest (AESI). The abnormal laboratory values should be confirmed by repeated measurements as soon as possible (i.e., within 7 days after the first observation) at local or central laboratory. Regarding any subject who meets the AESI criteria, the Investigator should discuss with the Sponsor Medical Monitor about the determination of etiology and the possibility for suspension of dosing. Resumption of dosing will be considered based on the discussion with the Sponsor Medical Monitor and Investigator.

All hepatic AESIs (including event management and evaluation) will be recorded and reported similar to SAEs as described in Section 12.8.

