In embryo-fetal development study in mice, the total incidence of fetuses with skeletal anomalies was increased at [REDACTED], the lethal dose for adult female mice, with increased incidence of fused rib and fused sternebrae. In the rat pre- and postnatal development study (ongoing study), 2 dams died on lactation day (LD) 11 and LD 18 at [REDACTED]. The causal relationship of these deaths to MT-7117-treatment has not been established. In the F1 offspring, MT-7117 related toxicities were observed in the [REDACTED] group: a total litter loss of 2 dams, a significant increase or tendency towards an increase in deaths and cannibalism, and lower body weights.

Female subjects of child-bearing potential and male subjects with partners of child-bearing potential participating in the study will be required to use adequate contraception as defined in Section 8.7.1, and female subjects who are pregnant, lactating, or intending to become pregnant during the study are excluded from the study.

The Sponsor will undertake all reasonable measures, including thorough screening and safety monitoring procedures, to minimize the risk to subjects. Due to the potential of MT-7117 to increase liver function markers, liver function markers will be monitored at all planned study visits and assessment of AEs related to elevation of liver function markers and liver injury will be conducted. Additionally, subjects will be instructed to immediately stop study treatment if they meet any of the withdrawal criteria listed in Section 8.5.

Risk related to COVID-19 has been assessed. MT-7117 is not known to compromise the human immune system. In non-clinical repeated dose toxicity studies, there were no changes suggestive of immunosuppression. Completed Phase 1 and Phase 2 studies did not show increased risk of infection. Based on the evidence available so far, it is unlikely that MT-7117 exposure will increase the risk of COVID-19 infection; however, it is unknown if MT-7117 exposure will increase the risk of COVID-19 infection. There may be additional risk to participants due to exposure to COVID-19 during study related visits (depending on the country/region conditions).

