8.5 Withdrawal of Individual Subjects

A subject will be withdrawn from study if ANY of the following criteria are met:

1. The subject requests to voluntarily withdraw from further participation in study.
2. The subject is significantly noncompliant with the protocol.
3. Continuing in the study would be detrimental to the subject's safety in the opinion of the Investigator, e.g.,
 - a. The subject experiences intolerable AEs, SAEs, or AESIs.
 - b. The subject has clinically significant changes in safety parameters at any of the post-dose time points, as confirmed with a repeat assessment performed as soon as possible after the initial out-of-range result.
 - c. The subject experiences any clinically significant adverse findings from postbaseline nevi evaluation and adverse change is demonstrated histologically and confirmed by central pathologist. Visual evaluation of change will not be acceptable criteria for permanent discharge from treatment (Section 10.9.4).
 - d. Development of any clinically significant liver dysfunction, as follows:
 - i. ALT or AST $>8 \times$ ULN.
 - ii. ALT or AST $>5 \times$ ULN for more than 2 weeks.
 - iii. Elevated total bilirubin $>2 \times$ ULN and ALT or AST $>3 \times$ ULN or
 - iv. Symptoms consistent with liver dysfunction (e.g., fatigue, nausea, vomiting, abdominal pain or tenderness, fever, rash, eosinophilia $>5\%$) with concomitant ALT or AST values $>3 \times$ ULN.

Subjects meeting the laboratory criteria of ALT/AST and total bilirubin defined above (with or without alternative etiology), regardless of whether clinically significant or not, should be reported as a hepatic AE of special interest (AESI) (see Section 12.3). The Investigator should discuss with the Sponsor Medical Monitor about the determination of etiology and the potential of withdrawal. The abnormal laboratory values should be confirmed by repeated measurements at local or central laboratory as soon as possible (i.e., within 7 days after the first observation).

Any other laboratory or clinical abnormality that the Sponsor Medical Monitor and/or Investigator considered as clinically significant should be considered as potential reason for withdrawal.

These subjects will be discontinued from treatment but may be followed per protocol (see

Section 12.6). In addition, a subject may be withdrawn from treatment at any time for reason(s) other than those listed here. Subjects who have withdrawn from study drug cannot resume study drug.

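### When one of four shared liver criteria is first met, Protocol 7.3 calls for an immediate stop but 12.3.1 leaves suspension to an undated discussion, and no interim hold is written

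*Protocol*

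**What the plan says.** Sections 8.5 (item 3d, i to iv) and 12.3 give the same four criteria:

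- i: ALT or AST above 8 x ULN;
- ii: ALT or AST above 5 x ULN for more than 2 weeks;
- iii: total bilirubin above 2 x ULN together with ALT or AST above 3 x ULN;
- iv: symptoms of liver dysfunction together with ALT or AST above 3 x ULN.

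The dosing consequence is described in several places.

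- **Protocol 7.3:** "subjects will be instructed to immediately stop study treatment if they meet any of the withdrawal criteria listed in Section 8.5".
- **Protocol 8.5:** the liver criteria are examples under a test of the subject's "safety in the opinion of the Investigator, e.g", headed "Development of any clinically significant liver dysfunction, as follows". The text then says "The Investigator should discuss with the Sponsor Medical Monitor about the determination of etiology and the potential of withdrawal". Further on it says "These subjects will be discontinued from treatment but may be followed per protocol" and "Subjects who have withdrawn from study drug cannot resume study drug".
- **Protocol 12.3.1:** for any subject who meets the criteria for an event of special interest, "the Investigator should discuss with the Sponsor Medical Monitor about the determination of etiology and the possibility for suspension of dosing". It adds: "Resumption of dosing will be considered based on the discussion with the Sponsor Medical Monitor and Investigator".
- **Protocol 10.9.5.2:** refers to withdrawal criteria for raised liver tests, but prescribes only standard care and follow-up.
- **Protocol 12.3:** one bullet cites 8.5 for interruption of study drug, but 8.5 contains no interruption rule.

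Sections 8.5 and 12.3.1 both ask for a repeat measurement within 7 days of the first observation. Section 12.8 requires the event to be reported within 24 hours of the investigator becoming aware of it.

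**The concern.** An investigator who receives a result meeting one of these criteria needs to know whether the subject takes tomorrow's dose. Section 7.3 says no. Section 12.3.1, where a site would look for instructions, makes even suspension something to talk over first. Followed as written, it allows dosing to continue with ALT or AST above 8 x ULN, or with combined bilirubin and transaminase elevation, until the discussion takes place.

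What is at stake is safety conduct and consistency between sites. Liver dysfunction is the event of special interest that the protocol names. Section 7.3 cites the drug's potential to raise liver markers, and 7.2 reports abnormal hepatic markers in rats and monkeys. Samples at Visits 3, 5, 8 and 9 may be taken by a mobile unit and are shipped to a central laboratory, so the subject may be at home when the result arrives.

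**Working it through.** The plan gives no figure to reproduce. The check is a comparison of texts plus one small count.

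**1. Same trigger?** Yes. The four criteria in 8.5 (3d) and 12.3 match. Criteria i, iii and iv can be met on one blood sample (3 of 4); ii needs values over more than 2 weeks.

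**2. Same action?** No.

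| Section | Dosing action when a criterion is met | When |
|---|---|---|
| 7.3 | Stop | Immediately |
| 8.5 | Withdrawal discussed with the Medical Monitor | No deadline |
| 12.3.1 | Suspension discussed with the Medical Monitor | No deadline |
| 10.9.5.2 | None stated | Not stated |

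**3. Is the interval covered elsewhere?**

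- The 24-hour rule in 12.8 governs reporting, and nothing ties the Medical Monitor discussion to it.
- The 7-day limit governs the repeat test and carries no dosing instruction.
- The iDMC (13.5) reviews safety data regularly but does not set an individual subject's dosing.
- SAP 8.1.9 counts study drug suspension separately from permanent discontinuation, so suspensions were foreseen. The SAP gives no dosing rule.
- Section 10.9.4 writes the full sequence for suspicious nevi: temporary discontinuation, evaluation, then restart or permanent stop. No readable equivalent exists for the liver.

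**4. Illustration of the interval.** Dosing is once daily (11.2).

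- Section 7.3 followed: 0 further doses.
- Action delayed until a repeat test on day 7 after the first observation: up to 7 x 1 = 7 further doses.

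The second figure assumes that a site waits for the repeat and that the repeat is taken on the last permitted day. Laboratory turnaround is not given and is left out.

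**5. Price of an interim hold.** The double-blind period is 26 x 7 = 182 days.

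- False alarm resolved on day 7: 7/182 = 3.8% of daily doses.
- False alarm resolved on day 1: 1/182 = 0.5%.

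**The case against.** The strongest defence is that the sections form a sequence. Section 7.3 acts only on 8.5 criteria. Item 3 of 8.5 depends on investigator opinion and clinical significance. Section 12.3.1 covers a wider set, since 12.3 has two further categories. On this reading, subjects judged to meet 8.5 stop and the rest are discussed. The investigator may also withdraw treatment at any time, and the 24-hour report brings the sponsor in quickly.

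Part of this stands: a hold followed by a decision may well be what was intended. But 12.3.1 applies to every subject who meets the criteria, including clinically significant cases, and the readable text neither writes the sequence for the liver nor says which section takes precedence. The existing safeguards limit the risk without setting dosing in the interval.

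The objection also rules out several stronger readings that a reader might infer.

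- **That the protocol both forbids and permits restarting.** The bar in 8.5 applies to subjects withdrawn from study drug, while resumption in 12.3.1 follows a suspension. The two can be reconciled.
- **That 8.5 flatly orders discontinuation for all four criteria.** The sentence "These subjects will be discontinued from treatment but may be followed per protocol" follows a paragraph on other abnormalities, so it is unclear which subjects it means.
- **That 12.3.1 reaches results without clinical significance while 8.5 does not.** Both sections carry the same clause on clinical significance, and in both it concerns reporting.
- **That the protocol allows 7 more doses.** It does not. The count depends on assumed timing, requires 7.3 to be disregarded, and runs from first observation, whereas the 24-hour reporting clock runs from investigator awareness.

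**Conclusion.** The inconsistency is real but narrow. For four shared liver criteria, 7.3 requires an immediate stop, while 12.3.1 and the discussion sentence in 8.5 leave suspension or withdrawal to a conversation with no deadline. No readable global text holds dosing until that conversation or the repeat test.

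The consequence lies in safety conduct. The primary estimand uses a treatment-policy strategy for discontinuation, so its definition is unaffected. Few subjects are likely to be involved: the documents give no expected number, and Protocol 5.2 reports no trend in hepatic adverse events in Phase 2.

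The conclusion rests on the readable global protocol and SAP. The redacted appendices and the Japan, Norway, Germany and Canada protocols could not be checked and may already contain a rule. The point is best classed as a cheap improvement.

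**What to change.** In 12.3.1 add, for the four liver dysfunction criteria only:

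> *Study drug is held immediately when any of these criteria is first observed, in line with Section 7.3, pending the repeat test and the Medical Monitor discussion, both within 7 days. Subjects then judged to meet Section 8.5 are permanently withdrawn from study drug and cannot resume. Otherwise, resumption requires the Medical Monitor's documented agreement.*

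Add a cross-reference to this hold in 8.5, in 10.9.5.2 and in the interruption bullet of 12.3. Leave the 8.5 withdrawal criteria and the bar on resumption after withdrawal as they are. Turning withdrawal itself into a hold with possible restart would be a separate and debatable safety decision, and this point does not need it.

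The fix is a wording change. It needs no new test or visit, because the repeat test and the discussion already exist; only the discussion gains a deadline. The downside is the missed doses in a false alarm, as calculated above. Laboratory turnaround would add to them if the decision waits for the repeat result. The country-specific protocols may need the same wording.

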12.4 Severity of Adverse Events

The severity of AEs will be classified according to the following criteria:

Mild:	The event is transient and easily tolerated by the subject.
Moderate:	The event causes discomfort and interferes with the subject's general condition.
Severe:	The event causes considerable interference with the subject's general condition and may be incapacitating.

To ensure no confusion or misunderstanding of the difference between the terms 'serious' and 'severe', which are not synonymous, the following note of clarification is provided:

The term 'severe' is often used to describe the severity of a specific event (as in mild, moderate, or severe myocardial infarction); the event itself, however, may be of relatively minor medical significance (such as severe headache). This will not be the same as 'serious', which will be based on subject/event outcome or action criteria usually associated with events that would pose a threat to a subject's life or functioning. Seriousness (not severity) will serve as a guide for defining regulatory reporting obligations.

12.5 Relationship of Adverse Events to Investigational Medicinal Product

The causal relationship of the AE to study medication will be determined as either 'a reasonable possibility' or 'no reasonable possibility,' and will be defined as having either one of the following:

- **A Reasonable Possibility** – The relationship of the clinical event to the study medication makes a causal relationship possible, and other drugs, therapeutic interventions, or underlying conditions do not provide a sufficient explanation for the observed event.
- **No Reasonable Possibility** – The relationship of the clinical event to the study medication makes a causal relationship unlikely, or other drugs, therapeutic interventions or underlying conditions provide a sufficient explanation for the observed event.

12.6 Clinical Laboratory Abnormalities, and Other Abnormal Assessments

The Investigator will exercise medical judgment in deciding whether abnormal laboratory test results are clinically significant. Laboratory abnormalities which are clinically significant will be recorded as AEs or SAEs.

If an abnormal laboratory value or assessment is clearly related to a medically-defined diagnosis or syndrome, the diagnosis or syndrome will be recorded on the AE form, not the individual laboratory values.

All 'abnormal, clinically significant' laboratory results or assessments will be followed until they resolve (return to normal or baseline values) or stabilize, or until they are judged by the

Investigator to be no longer clinically significant. Repeat laboratory tests or measurements will be performed if needed.

The criteria for determining whether an abnormal objective test result should be reported as an AE include:

1. Test result is associated with accompanying symptoms, and/or
2. Test result requires additional diagnostic testing or medical/surgical intervention, and/or
3. Test result leads to discontinuation from the study, significant additional concomitant drug treatment, or other therapy, and/or
4. Test result is considered to be an AE by the Investigator or Sponsor.

12.7 Recording and Reporting of Adverse Events

All AEs, regardless of the relationship to study medication, occurring from the time written informed consent/assent is obtained from a subject until the end of the safety follow-up period or the withdrawal of the subject from the study, and any AEs or SAEs reported spontaneously through the end of the safety follow-up period, should be reported to the Sponsor or designee.

NOTE: elective hospitalization or procedure/surgery planned before subject enrollment for a preexisting medical condition does not constitute an AE unless the underlying disease or condition worsens after signing informed consent/assent.

At each study visit, after the subject has had an opportunity to spontaneously mention any problems, the Investigator should inquire about the occurrence of AEs. The questioning will be open-ended and non-leading.

All AEs will be recorded in the source documents and AE eCRF. The AE eCRF will contain a description of the event, date of onset, date of resolution, severity, treatment required, relationship to study medication, action taken with the study medication, outcome, and whether the event is classified as serious.

The Investigator will evaluate the severity of the AEs (as defined in Section 12.4) and will assess the causality between the AEs and the study medication (as defined in Section 12.5).

Pre-existing illnesses, which started before entry and is still ongoing at the start of the study, will not be considered AEs unless they worsen during the treatment period. Pre-existing conditions will be recorded as medical history.

If the Investigator becomes aware of any new safety information, or any safety information which appears to be either study or study medication related after the final follow-up period, then they must notify the Sponsor or the designee immediately.

12.8 Recording and Reporting of Serious Adverse Events or Hepatic Adverse Events of Special Interest

All SAEs and Hepatic AESI occurring from the time written informed consent/assent is

obtained from a subject until the end of the safety follow-up period or the withdrawal of the subject from the study must be reported to the Sponsor or the designee using the *Serious Adverse Event/Adverse Event of Special Interest (SAE/AESI) in a Clinical Study Form* within 24 hours of the Investigator becoming aware of the SAE/AESI. All SAE/AESIs must also be entered in the AE section of the eCRF as soon as possible.

The SAE/AESI report should be completed as thoroughly as possible, including an assessment of causality. All such reports will identify subjects by unique code numbers assigned to the study participants, rather than by the subjects' names, personal identification numbers, or addresses.

The reporting contact for SAE/AESIs by email is as follows:

Email: [REDACTED]

In case of any email problems, the SAE/AESI form will be sent to [REDACTED] via fax to:

Fax: [REDACTED]

Reports of pregnancy, although not classified as an SAE, will be handled and reported as in Section 12.9.

The Sponsor will comply with the applicable regulatory requirements related to the reporting of suspected unexpected serious adverse reactions (SUSARs) to the Regulatory Authorities and central IRB/IEC(s). The Investigator will be responsible for informing the local IRB/IEC(s) of SUSARs, as per local laws and requirements.

